4.7.1 Adverse Events

Adverse events will be summarized in terms of treatment-emergent adverse events (TEAEs) where treatment-emergent is defined as any AE that occurs after administration of the first dose of study drug and through 28 days after the last dose of study drug, any event that is considered study drug-related regardless of the start date of the event, or any event that is present at baseline but worsens in intensity or is subsequently considered study drug-related by the Investigator. Treatment-related TEAEs include those events considered by the investigator to be possibly, probably, or definitely related to study drug.

Adverse Events will be coded using MedDRA version 17.0 and graded according to the National Cancer Institute (NCI) Common Terminology Criteria for Adverse Events (CTCAE) v4.03. The incidence of TEAEs will be summarized by MedDRA System Organ Class (SOC), Preferred Term (PT) and NCI CTCAE grade. Tables summarizing the incidence of TEAEs will be generated for each of the following:

- Treatment Emergent AE Overview;
- All TEAEs by SOC and PT;
- TEAE by SOC, PT, and CTCAE Grade
- Treatment-Related TEAEs by SOC and PT;

TPBS001 Version 6 CONFIDENTIAL Effective Date: 15th March 2017 (based on TPQA036 Version 2) Prior Effective Date: 9th October 2016

| Sponsor: | Almac | Protocol Number: | ALM201/0001 |
|----------|-------|------------------|-------------|

- Treatment-Related TEAEs by SOC, PT and CTCAE grade;
- Treatment Emergent Serious Adverse Events by SOC and PT;
- Treatment Emergent Serious Adverse Events by SOC, PT and CTCAE grade;
- Treatment-Related Treatment Emergent Serious AEs by SOC and PT;
- Treatment-Related Treatment Emergent Serious Adverse Events by SOC, PT and CTCAE grade;
- Treatment-Emergent Adverse Events ≥ Grade 3 by SOC and PT
- Treatment-Related Treatment-Emergent Adverse Events ≥ Grade 3 by SOC and PT
- TEAEs leading to discontinuation of study drug by SOC and PT
- TEAEs leading to modification/interruption of study drug by SOC and PT
- Dose Limiting Toxicities by SOC and PT
- Fatal TEAEs by SOC and PT

If a patient experiences multiple episodes of the same event, the patient will only be counted once for that particular event. In the case of partially missing AE start dates, all available date information will be used to determine whether or not the AE is treatment-emergent. Adverse events with completely missing start dates will be considered to be treatment-emergent unless the stop date is known to be prior to the first administration of the study drug.

For tables that are presented by maximum grade, if a patient experiences multiple episodes of the same event, the event with the maximum grade will be used.

For tables that are presented by strongest relationship, if a patient experiences multiple episodes of the same event, the event with the strongest relationship to study drug will be used.

Deaths, serious adverse events (SAEs), and AEs resulting in study drug discontinuation also will be tabulated. The AE summaries will be presented in alphabetical order of SOC and preferred term.

All AEs, including treatment-emergent and non-treatment-emergent AEs, will be presented in data listings.

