Note that the MTD or MFD need not be confirmed for the original dose administration schedule prior to the CRC recommending the investigation of an alternative dose administration schedule. Multiple dose escalation tracks may be followed if more than one dose schedule is considered relevant to explore i.e. the CRC may recommend that the alternative dose administration schedule

replaces a schedule or is explored in addition to another schedule, as long as dose escalation rules are not exceeded.

Duration of treatment

The main study will permit a maximum of 8 three-weekly treatment cycles (or approximately 6 months of treatment). Patients who are seen to potentially be benefiting from treatment i.e. patients whose disease has not progressed and who have not been withdrawn from therapy due to toxicity, will be eligible to continue to receive additional cycles of ALM201 where this is recommended by their study physician, subject to availability of ALM201. Such patients will continue to be followed up for compliance, toxicity and continued response ([Schedule of Study Assessments](#)).

Part 2: Enrichment at MTD, MFD and/or BAD

Once an MTD, MFD and/or BAD has been established for a given dose and schedule in Part 1, Part 2 may commence. Part 2 will involve up to an additional 36 patients with advanced ovarian cancer. During Part 2 of the study there will be on-going evaluation of safety and the opportunity to obtain preliminary anti-tumour activity at each dose level selected in the ovarian cancer population. The only dose adjustments permitted in Part 2 will be dose de-escalations (based on a de-escalation of the unit dose or a less frequent administration schedule of the maximum unit dose). Such decisions will be driven by each patient's tolerability of ALM201. Where possible, such dose reductions should be made by the CRC who can convene on an ad-hoc basis to advise on the appropriate dose adjustment; however, the investigator may implement a dose reduction prior to CRC review in the interest of patient safety.

Study Assessments:

The study will commence with a dosing schedule of ALM201 monotherapy given SC on Days 1-5, 8-12 and 15-19 in a 3 week cycle.

Patients will have scheduled site visits on every dosing day of the first cycle, then on Days 1, 8 and 15 of Cycles 2-4. From Cycle 5 onwards, they are only required to visit the clinic on Day 1 of each cycle. ALM201 administration can be given at home on all other days.

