3.5 Study Analysis Populations

Enrolled Patients: All patients who enroll in the trial.

Efficacy Population: All patients with at least one post-baseline tumour response assessment

Safety Population: All patients who receive at least one dose of study drug.

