3.7 Sample Size

No formal sample size calculation was performed.

CONFIDENTIAL

4 Statistical Methodology

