4.1 Analysis Conventions

This section details general conventions to be used for the statistical analyses. Departures from these general conventions may be given in the specific detailed sections of this analysis plan. All data were collected using electronic case report forms (eCRFs).

- For all analyses, each dose level and overall will be summarized using descriptive summary statistics. Each treatment group will have a cohort number and data will be summarized in all tables, listings, and figures by treatment or cohort number. No statistical comparison of dose levels will be performed.
- Summary statistics will consist of the number and percentage for categorical variables, and the number of observations (n), mean, standard deviation (Sd), minimum, median, and maximum values for continuous variables. When the standard deviation cannot be calculated, a hyphen (-) will be used.
- All mean and median values will be formatted to one more decimal place than the
 measured value on the eCRF. Standard deviation values will be formatted to two more
 decimal places than the measured value on the eCRF. Minimum and maximum values
 will be presented with the same number of decimal places as the measured value on the
 eCRF.
- The number and percentages will be presented in the form XX (XX) where the percentage is in the parentheses. Unless otherwise specified, the denominator for percentages will be the number of patients in a given dose level within the analysis population of interest.
- All summary tables will include the analysis set sample size (i.e., number of patients).
- Baseline is defined as the last planned assessment before the first administration of study drug, unless otherwise specified. Typically this will be the Cycle 1 Day.
- Change from baseline will be calculated as follows:

Change from baseline = Post-baseline value – baseline value.

- Age will be calculated as the integer: (Date of informed consent date of birth)/365.25, rounded down to the nearest integer.
- Duration of time on study drug (days) = Date of last injection date of first injection+1.
- Date and time variables will be formatted as DDMMMYYYY hh:mm for presentation.

TPBS001 Version 6 (based on TPQA036 Version 2)

CONFIDENTIAL

| Sponsor: | Almac | Protocol Number: | ALM201/0001 |
|----------|-------|------------------|-------------|
| | | | |

- Summary tables with present data from scheduled assessments; listings will include all data, sorted by date.

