4.7 Analyses of Safety and Tolerability

All safety analysis will be performed on Safety Population.

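### Apart from the Cycle 1 DLT table, the by-dose TEAE percentages cover each patient's whole time on drug plus 28 days, so they mix dose with time at risk if treatment duration differs between cohorts

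*SAP*

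**What the plan says.** The measure is set in SAP 4.7.1: "The incidence of TEAEs will be summarized by MedDRA System Organ Class (SOC), Preferred Term (PT) and NCI CTCAE grade". A patient with repeated episodes counts once. An event is treatment-emergent if it starts after the first dose and within 28 days of the last. Drug-related events count whatever their start date, as do baseline events that worsen.

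SAP 4.1 sets the layout: "For all analyses, each dose level and overall will be summarized using descriptive summary statistics". Unless stated otherwise, percentages use the number of patients at the dose level as denominator, not patient-time or cycles.

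The population is fixed by SAP 4.7, "All safety analysis will be performed on Safety Population", and SAP 3.5, "Safety Population: All patients who receive at least one dose of study drug". At the other end, the Protocol synopsis (Duration of treatment) says: "The main study will permit a maximum of 8 three-weekly treatment cycles". It then lets patients without progression or withdrawal for toxicity carry on, with no stated upper limit.

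SAP 4.7.1 lists 15 tables. One is the DLT table, and the Protocol synopsis (Dose Limiting Toxicity) restricts DLTs to the first cycle. No other AE table is limited to Cycle 1 or split by cycle, and no exposure-adjusted rate or time-to-event summary is planned. Exposure (SAP 4.4) and the count of patients dosed in each cycle (SAP 4.2) are reported separately.

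**The concern.** Safety and tolerability is the only primary objective in the SAP, and Part 1 is now the final analysis. The by-dose AE tables are where a reader will look for how toxicity changes with dose. Under the planned definition, the chance of appearing in such a table grows with time on treatment. Disease progression is the first example reason for discontinuation in SAP 3.6.1, so duration depends at least partly on something other than dose.

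Cohorts may hold 1 to 6 patients. One long-treated patient at a low dose could therefore make that dose look worse than a higher dose at which patients stopped early.

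The DLT table does not fill this gap. A DLT is a Grade 3 or 4 event that the Cohort Review Committee (CRC) judges likely related and clinically hazardous, with exceptions, or a related dose delay of more than 14 days. Grade 1 and 2 events are left out, including the related Grade 2 events that the committee uses when deciding to enlarge cohorts.

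**Working it through.** **The plan's own figure.** 8 cycles × 21 days / 7 = 24.0 weeks. This agrees with the first 24 weeks given for Cycles 1 to 8 in the Protocol synopsis (Study Assessments) and SAP 3.2. There is no power calculation to reproduce: "No formal sample size calculation was performed".

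**Time at risk.** On the weekday schedule the last dose of cycle c falls on day 21(c − 1) + 19. Using the SAP 4.1 definition of duration (last injection − first injection + 1), the TEAE window is days on drug + 28.

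**Illustrative incidence.** Assume a risk p per 21-day cycle that is the same at every dose, constant over time, and continues at the same rate through the 28-day tail. Then the rate is λ = −ln(1 − p)/21 and the expected incidence is 1 − exp(−λ × window). The documents give no p, so a range is shown.

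| Treatment | Days on drug | Window (days) | p = 5% | p = 10% | p = 20% |
|---|---|---|---|---|---|
| 1 dose | 1 | 29 | 6.8% | 13.5% | 26.5% |
| 1 cycle | 19 | 47 | 10.8% | 21.0% | 39.3% |
| 2 cycles | 40 | 68 | 15.3% | 28.9% | 51.4% |
| 4 cycles | 82 | 110 | 23.6% | 42.4% | 68.9% |
| 8 cycles | 166 | 194 | 37.7% | 62.2% | 87.3% |
| 12 cycles | 250 | 278 | 49.3% | 75.2% | 94.8% |

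Example at p = 10%: λ = 0.10536/21 = 0.005017 per day. For 2 cycles, 1 − exp(−0.005017 × 68) = 28.9%. For 8 cycles, 1 − exp(−0.005017 × 194) = 62.2%. The 8-to-2-cycle ratios at p = 5%, 10% and 20% are about 2.5, 2.2 and 1.7.

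**Fixed versus mean duration.** These figures assume that every patient in a cohort has the same duration. The function is concave, so a spread of durations lowers the incidence. Half at 2 cycles and half at 14 (window 292 + 28 = 320 days, 79.9%) also averages 8 cycles, but gives (28.9 + 79.9)/2 = 54.4%, not 62.2%.

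**Can the order reverse?** Assume dose A has 10% risk per cycle for 8 cycles, dose B has 20% for 2 cycles, and each has 6 patients. The expected all-cycle incidence is 62.2% for A and 51.4% for B. Summing Bin(i; 6, 0.622) × Bin(j; 6, 0.514) over j < i gives a probability of 0.54 that B, the more toxic dose per cycle, shows fewer affected patients. Limited to Cycle 1, the expected incidence is 10% for A and 20% for B, and the same sum gives 0.17.

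**The case against.** The case against acting has real weight.

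- **The tables are descriptive.** SAP 4.1 says: "No statistical comparison of dose levels will be performed". The recommended phase 2 dose objective is no longer in the SAP, and escalation was decided by the CRC, primarily on Cycle 1 DLTs. No decision in the SAP rests on ranking doses by these percentages. This stands and limits the severity. But a table with one column per dose is read across its columns whether or not a test is run.
- **Much of the information is already planned.** Exposure and patients dosed per cycle are reported, and every AE is listed. Laboratory values, vital signs and ECGs are summarised by time point, and ECOG status by cycle. So the gap is in the AE tables only, and a reader could roughly rebuild the picture from the listings. Nothing planned links exposure to the AE percentages, however.
- **Duration may have no systematic link with dose.** If disease sets it, only chance imbalance remains. That is fair, but in cohorts of 1 to 6 chance imbalance can be large.
- **Cycle 1 tables have limits.** They are just as imprecise (a one-patient cohort shows 0% or 100%) and say nothing about late toxicity. The SAP 2.4 primary endpoint covers AEs during treatment and follow-up, and the Protocol requires trends in later cycles to be considered. This also stands, and it is why the Cycle 1 tables should supplement the planned ones.

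A reader might go further and infer that no AE table uses a common window. The DLT table does. A reader might also count on-drug cycles only, 1 − 0.9² = 19% against 1 − 0.9⁸ = 57%, and claim a three-fold distortion. That omits the 28 days the SAP counts, and would need the risk to vanish once dosing ends, which the documents do not say.

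**Conclusion.** The point holds in a limited form. Fourteen of the 15 tables give crude per-patient incidence over individual windows that can run from 29 days (one dose) to 194 days (8 cycles) or more, and the plan has no AE table that separates dose from duration. With equal risk per cycle, cohorts treated for 2 and 8 cycles would show roughly a two-fold difference: about 29% against 62% at 10% per cycle, and 51% against 87% at 20%. These sizes rest on assumed risks and durations, a constant rate that continues through the tail, and equal duration within a cohort.

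A reader might infer that the reported dose pattern will be confounded. The documents do not support that: distortion arises only if durations differ between cohorts, and no durations are given. Nothing in the plan is contradictory or wrong. This is a cheap improvement to the reporting of the primary objective.

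**What to change.** In SAP 4.7.1 add two tables by dose level:

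1. TEAEs with onset in Cycle 1, by SOC, PT and maximum grade.
2. The same for related TEAEs of Grade 3 or higher.

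State whether Cycle 1 closes at Day 21 or at the first dose of Cycle 2, since a dose delay separates the two. Add a rule for incomplete start dates: the current rule classes an event with a wholly missing start date as treatment-emergent, unless it is known to have stopped before first dose, but does not place it in a cycle.

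Keep the all-cycle tables as planned, because they carry later and cumulative toxicity, and show the number of cycles started per dose level in their headers. Present the two sets side by side.

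The cost is two extra runs of existing tables with an onset-date filter, plus the date rule, and no new data. The Cycle 1 tables give a common onset window, not equal dosing: the Safety Population includes patients who stopped after one dose.

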4.7.2 Laboratory Measurements

Scheduled clinical chemistry, hematology, coagulation, urinalysis and tumour biomarker, and other laboratory assessments will be collected and analyzed according to the study center's standard procedure. The laboratory assessments collected will be the following:

| Clinical chemistry | Haematology, i | Haematology, including coagulation screen | | |
|--|----------------|---|--|--|
| Calcium | Red cell count | _ | | |
| Total protein | Hemoglobin | Hemoglobin | | |
| Albumin | Hematocrit | | | |
| TPBS001 Version 6 (based on TPQA036 Version 2) | CONFIDENTIAL | Effective Date: 15 th March 2017 Prior Effective Date: 9 th October 2016 | | |

| Clinical chemistry | Haematology, including coagulation screen |
|--|--|
| Total bilirubin | Absolute reticulocyte count |
| Alanine transaminase (ALT, SGPT) | Platelet count |
| Aspartate transaminase (AST, SGOT) | White blood cells |
| Alkaline phosphatase | Leucocyte differential count (% & absolute) |
| Glucose (random) | International normalized ratio or prothrombin time |
| Sodium | Activated partial thromboplastin time |
| Potassium | |
| Bicarbonate | |
| Chloride | |
| Magnesium | |
| Urea | |
| Creatinine | |
| Phosphate | |
| Uric acid | |
| Pregnancy test as required (Screening) | - |

Urinalysis Glucose* Protein* Bilirubin* Ketones* Blood* pH Specific gravity &

Microscopic examination when indicated

Pregnancy test as required

* Assessed categorically only

| Creatinine clearan | ce should b | e calculated | using the | Cockroft-0 | Gault Fo | ormula, v | which is | s given l | belo | OW: |
|--------------------|-------------|--------------|-----------|------------|----------|-----------|----------|-----------|------|-----|
|--------------------|-------------|--------------|-----------|------------|----------|-----------|----------|-----------|------|-----|

1.25 x (140 – age) x weight (kg)

Males:

Serum creatinine (μmol/l)

1.05 x (140 – age) x weight (kg)

Females:

Serum creatinine (µmol/l)

TPBS001 Version 6 (based on TPQA036 Version 2)

CONFIDENTIAL

| Sponsor: | Almac | Protocol Number: | ALM201/0001 |
|----------|-------|------------------|-------------|
| | | | |

Cockroft DGM, 1976iii

Lab values will be expressed in SI units. Any lab data collected from local labs that are nont in SI units will be converted in the analysis dataset to SI units prior to summarization. Actual and change from baseline summary statistics will be presented at each scheduled time point of the study for each lab parameter. Laboratory parameters with categorical results will be summarized with the number and percentage of patients. Repeat and unscheduled measurements will not be summarized; however, they will be in the data listings.

Shift tables from baseline result to worst post-baseline result will be generated. In the shift tables, results will be categorized as low, normal, high, including low clinically significant and high clinically significant when available. If a patient has both low and high post-baseline values, the summary table will display the result with the greatest absolute departure from the normal limits for that parameter. The denominators for the percentages will be the number of patients with non-missing data at both the baseline and any post-baseline time point for a parameter.

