Upon occurrence of the first DLT in any cohort, additional patients will be added to that cohort so that up to a total of 6 can be evaluated. Once expansion to a 6-patient cohort has been recommended due to the identification of a DLT, escalation to the next 3-patient cohort will only occur when all patients in the expanded cohort have completed their first cycle of ALM201 and no more than 1 DLT has occurred. If 2 or more DLTs occur in an expanded cohort, DLT is established and the next lower dose level will be declared the MTD.

The highest dose where ≤ 1 DLT is seen in 3 or 6 patients will be termed the MTD. Note that intermediate dose levels may be explored below the dose level where ≥ 2 DLTs were seen, in order to identify the maximum dose which may be adequately tolerated. The CRC may also specify a recruitment stagger to be followed during cohort expansion for DLT evaluation depending on the nature of the DLT and the considered risk to patients.

In the case where an MTD is not established, the maximum feasible single dose which may be administered will be dictated by the formulation of ALM201 and the maximum volume for SC administration i.e. 3 x 1 mL injections, which will administer a dose of 300 mg ALM201 ([Section 6](#)). Should this dose be reached without the need to de-escalate due to DLT, it will be termed the MFD.

Based on the review of PD data in conjunction with on-going safety and PK data, the CRC may also identify a BAD for further exploration in Part 2 of the study.

Safety evaluations will be conducted weekly during each treatment cycle, with DLT assessed during Cycle 1 only. All events and suspected DLTs will be graded according to the CTCAE v4.03.

A DLT is defined as a Grade 3 or 4 AE that, in the opinion of the CRC, is likely to be related to ALM201 and represents a clinically significant hazard to the subject. Qualifying DLT events must be considered to be clinically relevant e.g. in duration, apparent reversibility, required management, and upon consideration of the patient's medical history and/or concomitant medications. DLT events must also be evaluated in terms of what is considered to be an appropriate next escalation step: in the case where the CRC agree that an escalation step of approximately 33% or lower is merited, the toxicity of concern should be declared a DLT.

Examples of exceptions that will be considered by the CRC are as follows:

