6. Eastern Collaborative Oncology Group (ECOG) Performance Status (PS) of 0 or 1 ([Appendix A](#)).
7. Laboratory values at Screening:
 - Absolute neutrophil count $\geq 1.5 \times 10^9/L$ without colony stimulating factor support;
 - Platelets $\geq 100 \times 10^9/L$;
 - Haemoglobin ≥ 9 g/dL (not transfusion dependent);
 - Total bilirubin < 1.5 times the upper limit of normal (ULN) (unless due to Gilbert's syndrome where it should be $\leq 2.5 \times$ ULN);
 - AST (SGOT) ≤ 2.5 times the ULN; ALT (SGPT) ≤ 2.5 times the ULN; $\leq 5 \times$ ULN for patients with advanced solid tumours with liver metastases; patients with confirmed bony metastases will be permitted on study with isolated elevations in ALP < 5 times the ULN;
 - Serum creatinine $\leq 1.5 \times$ ULN or estimated glomerular filtration rate (GFR) of > 50 mL/min based on the Cockcroft-Gault formula ([Appendix D](#));
 - Normal coagulation (elevated INR, prothrombin time or APTT $\leq 1.3 \times$ ULN range acceptable);
 - Urine protein $\leq 2+$ (as measured by dipstick).
8. Negative urine or blood human chorionic gonadotropin (hCG) test during Screening and within 7 days of Cycle 1, Day 1 in women of childbearing potential (defined as women ≤ 50 years of age or history of amenorrhea for ≤ 12 months prior to study entry). Sexually active male and female patients of childbearing potential must agree to use an effective method of birth control e.g. barrier methods with spermicides, oral or parenteral contraceptives and/or intrauterine devices, during the entire duration of the study and for 6 months after final administration of ALM201. Note that sterility in female patients must be confirmed in the patients' medical records and can be defined as any of the following: surgical hysterectomy with bilateral oophorectomy, natural menopause with menses > 1 year ago; radiation induced oophorectomy with last menses > 1 year ago; chemotherapy induced menopause with 1 year interval since last menses.

9. Ability to give written, informed consent prior to any study-specific Screening procedures, with the understanding that the consent may be withdrawn by the patient at any time without prejudice.
10. Patient is capable of understanding the protocol requirements, is willing and able to comply with the study protocol procedures, and has signed the informed consent document.

Exclusion Criteria for all Patients

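### Laboratory shift tables separate severity within low or high only by an undefined, conditional clinical-significance flag, so same-direction worsening in patients who enter out of range may show no shift

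*SAP*

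**What the plan says.** SAP 4.7.2 states: "Shift tables from baseline result to worst post-baseline result will be generated". On the categories it says: "In the shift tables, results will be categorized as low, normal, high, including low clinically significant and high clinically significant when available". The SAP does not say what makes a laboratory value clinically significant, who decides, or for which parameters or sites the flag will exist. Under SAP 4.1, "Baseline is defined as the last planned assessment before the first administration of study drug, unless otherwise specified".

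SAP 4.7.2 also plans summaries of actual values and changes from baseline by scheduled time point. Repeat and unscheduled results are listed but not summarised. SAP 4.7.1 applies CTCAE v4.03 grades to adverse events; no laboratory output uses them.

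Inclusion 7 in the protocol synopsis sets the laboratory limits for entry, several of them above the normal range. One example is ALP: "patients with confirmed bony metastases will be permitted on study with isolated elevations in ALP" below 5 x ULN. Inclusion 5 exempts lymphopenia from the requirement to recover from earlier treatment toxicity, and the SAP 4.7.2 laboratory panel includes the absolute leucocyte differential. The protocol's own severity scale is given under Dose Limiting Toxicity: "All events and suspected DLTs will be graded according to the CTCAE v4.03".

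**The concern.** A shift table shows change only when a patient moves from one category to another. A patient whose baseline is already high has no further category on that side except high with the clinical-significance flag. If the flag is missing or does not change, a large rise and no change at all fall in the same cell.

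Safety and tolerability is the only primary objective in SAP 2.1, and the study stopped after Part 1, so no Part 2 data will supplement this analysis. A laboratory signal by dose level that is confined to patients with abnormal baselines could be absent from the one display built to show each patient's worst change.

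**Working it through.** The plan gives no figure to reproduce here, so the check applies its category rule to patients at the entry limits.

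**Inputs.** The limits come from Inclusion 7. Bilirubin and ALP have strict upper bounds (below 1.5 and below 5 x ULN), so 1.49 and 4.9 are used. The entry limits apply at screening; the example assumes that the SAP baseline equals the limit. The fourfold rise is also an assumption, chosen for illustration.

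**Rule (high side).** A value up to 1 x ULN is normal; above that it is high, or high CS if flagged clinically significant. Worst value = 4 x baseline.

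| Parameter | Baseline (x ULN) | Worst (x ULN) | Category without flag |
|---|---|---|---|
| Bilirubin | 1.49 | 4 x 1.49 = 5.96 | high to high |
| AST/ALT | 2.5 | 4 x 2.5 = 10 | high to high |
| AST/ALT, liver metastases | 5 | 4 x 5 = 20 | high to high |
| ALP, bone metastases | 4.9 | 4 x 4.9 = 19.6 | high to high |
| Creatinine | 1.5 | 4 x 1.5 = 6 | high to high |
| INR/PT/APTT | 1.3 | 4 x 1.3 = 5.2 | high to high |

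Creatinine may be less bounded than the table suggests: Inclusion 7 accepts an estimated GFR above 50 mL/min as an alternative, and a patient who qualifies that way has no stated creatinine cap.

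**Effect of the flag.** The result is the same in all six rows:

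- No flag recorded: high to high, no shift.
- Not significant, then significant: high to high CS, a visible shift.
- Significant at both: high CS to high CS, no shift.
- Not significant at both: high to high, no shift.

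Three of the four patterns hide the rise. They are not equally likely, so this is not a probability. An ALT rise from 4 to 20 x ULN (20 / 4 = fivefold) in a patient with liver metastases behaves in the same way.

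**Low side.** Lymphopenic patients are admissible under Inclusion 5; they start low and without the flag cannot move lower. Haemoglobin is admitted from 9 g/dL, but the documents give no lower limit of normal. For any assumed limit from 11.5 to 13.5 g/dL, a fall from 9.0 to 6.5 g/dL is low to low without the flag.

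**What a patient weighs.** Part 1 cohorts have 1, 3 or 6 patients, so one patient is 1/1 = 100%, 1/3 = 33% or 1/6 = 17% of the cohort.

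**Comparison within the SAP.** SAP 4.7.5 lists its clinical-significance categories for ECG interpretations without an availability condition, and adds counts above two numeric QTcF thresholds, 450 and 470. Laboratory values get no numeric severity threshold.

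**The case against.** A reader might infer that the shift tables use three categories only. The text does not support that: the sentence on categories itself adds the clinically significant levels. A patient who goes from unflagged high to flagged high does shift, and the flag might well change in a case as marked as ALT from 4 to 20 x ULN.

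A reader might also infer that the plan cannot show severe laboratory toxicity. That too goes beyond the documents. SAP 4.1 includes the minimum and maximum among the statistics given per dose level, so in a small cohort the largest change at a scheduled visit is one patient's own value. SAP 4.7.1 tabulates graded adverse events, including those of Grade 3 or higher, and the listings hold every value. Dose decisions rest with the Cohort Review Committee, which reviews patient data and does not depend on the shift table. The Part 1 analysis is descriptive throughout.

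All of this stands, and it limits the point. It does not remove it:

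- A per-visit maximum shows at most the single most extreme patient. It does not count patients, is not expressed against the normal range or a grade, and leaves out repeat and unscheduled results.
- The graded adverse-event tables include a laboratory value only if it was reported as an event.
- The DLT table is not a backstop, because the protocol lists Grade 3 or 4 laboratory abnormalities that resolve or are corrected among the possible DLT exceptions.
- The listings give values without counts by dose.

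**Conclusion.** The point holds as a limitation of one display. For a patient who enters out of range, same-direction worsening appears in the shift table only if a clinical-significance flag exists and changes between baseline and worst value. Extreme values can be found elsewhere, but no planned table counts patients per dose level with new or worsened severe laboratory values independently of investigator judgement.

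The mechanism follows from the stated rule and the entry limits and does not depend on how common abnormal baselines are. The documents give no such rate, so no share of a cohort is claimed. The fourfold rise and the haemoglobin limits of normal are illustrative assumptions. The documents supplied do not reproduce the CTCAE thresholds, so the examples are not assigned grades.

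This affects how safety is reported, not how doses were escalated. It is an inexpensive improvement to the analysis of the sole primary objective.

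**What to change.** In SAP 4.7.2, for parameters with a CTCAE v4.03 grade, present shifts from baseline grade to worst post-baseline grade. Do this separately for the low and high directions, and derive the grade from the numeric value and the normal range. Add the number of patients per dose level with a new or worsened Grade 3 or higher value. State whether repeat and unscheduled results count towards the worst value in these tables.

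The existing range and clinical-significance shift can stay alongside, and remains the display for parameters without a grade. Where it is kept, define the flag: who assigns it, by what criterion, and for which parameters.

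The cost is SAP wording, some programming and extra tables. No new patient data are needed: classifying results as low or high, and measuring departure from the normal limits as SAP 4.7.2 already requires, presuppose that values and ranges are in the dataset.
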